
III. STUDY OBJECTIVES

To test Perception Threshold Tracking (PTT) and multi-level MRI as methods for early detection and grading of severity of neuropathy in patients with diabetes mellitus.

To use multi-level MRI for characterization of peripheral and central nervous system changes related to neuropathy in patients with diabetes mellitus.

To compare Perception Threshold Tracking (PTT) and MRI to methods of traditional clinical practice and established methods of clinical research like Corneal Confocal Microscopy (CCM) and Quantitative Sensory Testing (QST) as well as axon flair-mediated neurogenic vasodilation (AF).

To test reliability of different measurements of neuropathy.

A better understanding of the underlying neuropathy of diabetes and new methods for early, reliable detection of DPN could result in intensified treatment and prophylactic measures prolonging of the complicationfree period of diabetes mellitus. Ultimately, this could potentially result in fewer complications related to the diabetic foot, and maybe even prolonged overall-survival and reduced healthcare cost.

IV. METHODS

A. Study Design

This study is a prospective, observational, cross-sector study starting March 1, 2019 running until December 1, 2021. The study will be conducted on patients from Aalborg University Hospital. Participants will be informed about the trial both written and vocally and no changed in antidiabetic medication will be performed. The instruments will include Corneal Confocal Microscopy (CCM), Quantitative Sensory Testing (QST), axon flair-mediated neurogenic vasodilation (AF), handheld heart rate measurement device (Vagus[™]), cuff, and MRI, which are all established methods of clinical research. Furthermore, participants will be tested using monofilament and Biothesiometry, which equals actual clinical practice, and with Perception Threshold Tracking (PTT), which is a new take on an older, well-known technology. Further tests will include a handheld pinprick device, measurements of peripheral arterial disease (PAD) and conventional NCS. The main endpoint of the study will be sensitivity/specificity of all examinations, as well as a comparison of the newer methods against more well-established modalities.

B. Study Population

The study population include four well-defined groups of subjects:

- 1. Patients with Type 1 diabetes and painful diabetic peripheral neuropathy (DPN).

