- 2. Patients with Type 1 diabetes and non-painful diabetic peripheral neuropathy (DPN)
- 3. Patients with Type 1 diabetes and without diabetic peripheral neuropathy (DPN).
- 4. Healthy control subjects matched for age, BMI, and gender.

Diabetes duration, HbA1c, insulin use, ethnicity, and co-morbidities will be matched between group 1, 2 and 3 to best ability.

Inclusion criteria:

- 1. Men and women minimum 18 years of age and maximum 70 years of age
- 2. Signed informed consent form
- 3. Diagnosed with diabetes type I (for group 1-3)
- 4. Diagnosed with DPN defined as a threshold above 25-volt biothesiometry or absent feeling on the big toe using 10g-monofilament. (for group 1-2)
- 5. Answered questionnaire: PainDETECT
- 6. Nothing abnormal on initial tests (group 4)
- 7. Accepted initial screening blood samples
- 8. MRI-compatible participant

Exclusion criteria:

1. Current or previous alcohol- or drug abuse

- 2. Abnormal screening blood samples
- 3. Not being able to understand Danish written and/or verbally
- 4. Not being able to corporate to examination (e.g. not being able to speak, suffering from senile dementia etc.)
- 5. Previous chemotherapy or intake of experimental medicine
- 6. Active HSV- or VZV-infection or known HIV
- 7. Known severe skin disease
- 8. Known neural damage or disease in the neural system (e.g. MS, Guillain-Barre etc.)
- 9. Critical limb ischemia defined as in current clinical consensus[63]
- 10. Allergy or intolerance to histamine or inability to make do without for one day
- 11. Pregnancy
- 12. Active cancer-disease

C. Assessment of Resources

The study will be conducted in collaboration with Steno Diabetes Center Northern Denmark (SDCN) and Department of Radiology, Aalborg University Hospital. SDCN has access to patients with diabetes and can provide the necessary premises.

The study will be conducted in collaboration with Center for Neuroplasticity and Pain (CNAP), Aalborg University and SDCN, who have the technical and financial resources needed to establish the setup and conduct the examinations. Furthermore, an experienced research Bio. Med. Lab. Technologist is signed for the project thereby, alongside the Ph.D.-students, ensuring trained personnel. The study is set for a long inclusion, but additional time is available if required, as the Ph.D.-students are employed until 31st of October 2022.

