Quantitative Sensory Testing (QST) is a way of assessing large and small sensory nerve fiber function using several different stimuli. The method has been verified using different protocols, and will be conducted in

accordance to the original protocol by German Research Network on Neuropathic Pain (DFNS)[66]. All measurements are made on the dorsum of the foot. The test will be conducted by either PhD-students or research bio. med. lab. Technologist. The protocol consists of seven tests measuring 13 parameters including:

1) Thermal detection, thermal pain thresholds and paradoxical heat sensations:

The tests for thermal sensation will be performed using a thermal sensory testing device. Cold detection threshold (CDT) and warm detection threshold (WDT) are measured initially and the number of paradoxical heat sensations (PHS) are counted. Cold pain threshold (CPT) and heat pain threshold (HPT) are then calculated as a mean threshold temperature of three consecutive measurements. All thresholds are to be obtained with ramped stimuli increasing by 1 degree Celsius per second, terminated as the patient presses a button. Cut-off temperatures are set at zero and 50 degree Celsius and the baseline temperature is set at 32 degree Celsius, as this represents the mean value of skin temperature.

2) Mechanical detection threshold for modified von Frey filaments

Mechanical detection threshold (MDT) is to be measured using a standardized set of modified von Frey hairs that exert forces between 0.25 and 512 mN. The final threshold will be the geometric mean of five series of ascending and descending stimulus intensities.

3) Mechanical pain threshold for pinprick stimuli

Mechanical pain threshold (MPT) is to be measured using thin, blunt, weighted pinprick stimulators that exert forces between 8 and 512 mN. The set will consist of seven different stimulators and the MPT will be the mean of five series.

4) Mechanical pain sensitivity and dynamic mechanical allodynia

Mechanical pain sensitivity (MPS) is to be tested using the same weighted pinprick stimuli as for MPT (see above). To obtain a stimulus–response-function, the seven pinprick stimuli is applied in a balanced order, five times each, and the subject is asked to give a pain rating for each stimulus on a 0–100 numerical rating scale with 0 being no pain and 100 being worst pain imaginal.

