Axon flair-mediated neurogenic vasodilation (AF) uses Laser Doppler flowmetry (LDF) [66] or laser Doppler imaging (LDI) [67] to analyze vasomotor small fiber function by quantifying the integrity of the vasomotor-mediated axon reflex. While LDF assesses the flare response following acetylcholine iontophoresis with temporal resolution at a single defined skin point, LDI records flare responses with spatial and temporal resolution, generating a two-dimensional map of superficial blood flow [61]. In this study, the participants' surface skin temperature of the dorsum of the foot will be standardized to 32 degree Celsius using a warm blanket or warming pad. Either histamine or Acetylcholine will then be applied to a small area and vasodilation will be measured in accordance to earlier studies[67].

Estimated time: 15-20 min

Perception Threshold Tracking

Perception Threshold Tracking (PTT) is a potential new method for early detection of neuropathy. It is a further development of conventional threshold tracking[68] that excels in describing membrane potential of not only large, but also small nerve fibers[62]. The trial is conducted using two types of surface electrodes placed on the dorsum of the foot: patch and pin electrodes for stimulation of large and small nerve fibers respectively. The perception threshold is then estimated by slowly increasing the intensity of stimuli until the patient presses a button indicating that the stimuli is perceived. As this happens, the intensity is initially heighted by 20 % and then lowered until the patient relieves the button indicating that the stimulus is no longer felt. The intensity is then lowered by 20% and then increased until perception is indicated by pressing the button. This is repeated three to five times to increase precision. The perception threshold is taken as the average of the six to ten times the patient pressed the button. This procedure will be repeated a number of times using different electrodes. The patient will feel no significant pain, as the stimuli given is just around the individual perception threshold, which is a huge benefit of this method compared to other available neural tests.

Estimated time: 35-45 min

Multi-Level Magnetic Resonance Imaging

The multi-level MRI will be used to assess brain structure, function and metabolism and the peripheral nerve structure and function. The MRI session will consist of 1) an anatomical 3D scanning of the brain, 2) functional

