MRI scan, 3) whole brain diffusion tensor imaging (DTI) for assessment of microstructure and fiber tracts, 4) MR spectroscopy assessment of metabolite, 5) BOLD signal for microvascular function in central level and peripheral level, and 6) MRI neurography of the peripheral nerve fibers. Additionally, cuff occlusion procedure will be performed in the MRI scanner (cf. next section). Heart rate, respiration rate, will be recorded throughout the MRI scan.

Estimated time: 90 min

Cuff occlusion

During the BOLD-MRI a cuff occlusion procedure will be performed to investigate the microvascular function. A cuff will be mounted around the leg, proximal to the knee, and inflated (240 mmHg) for 5 minutes to reduce or blockage the blood flow in the lower leg.

Estimated time: 15 min

Cognitive Tests

A validated cognitive questionnaire will be performed to test the mild cognitive impairment and possible affected cognitive domains in the participants. Moreover, a cognitive task will be performed in the scanner in order to test the participants' cognitive psychomotor speed and memory.

Estimated time: 15-20 min

Vagus Test Procedure

A commercial available handheld device (Vagus[™], Medicus Engineering Aps, Aarhus N, Denmark) will be used to test the autonomic nervous system and hereby the autonomic neuropathy. The participant will hold the device during four steps, where the device will 1) measure the heart rate at rest, 2) measure the heart rate response from laying position to standing position, 3) measure the relationship between heart rate during expiration and inspiration, and 4) measure the heart rate conditions during exhalation with a resistance of 40mmHg and at rest.

Estimated time: 10-15 min

Blood samples

Blood samples will be taken after informed consent has been signed. Blood taken is estimated not to exceed 15 ml and will include:

Hgb, leukocytes and diff. counting, blood platelets, cobalamin, folate, sodium, potassium, creatinine, bicarbonate, CRP, ALAT, alkaline phosphatase, LDH, bilirubin, albumin, coagulation factors, vitamin D 1.25, Calcium-ion, TSH, HbA1c and M-component.

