To avoid 'mass significance' a combined analysis of all measurements will be performed by logistic regression models (LRM) in three steps. This will allow an estimate of the odds ratio and accuracy of each of the measurements and the measurements in combination. First, a series of univariate LRM will be performed for each measurement to investigate the odds ratio and accuracy of the individual. Second, a multiple factor LRM with all measurements as factors will be performed to estimate the odds ratio and accuracy for all measures in combination. Thirdly, factor reduction will be performed to assess the accuracy and odds ratio of a set of independent measures.

Simple bivariate correlation will be performed to further investigate the relation between measurements. Due to the complexity of the measurements a further analysis of the interdependency of the measures using factor analysis will be performed.

VII. DATA AND SAFETY MONITORING PLAN

The project will be reported to the Data protection Agency (DPA), and all sensitive data will be stored in either Red-CAP or on the protected server of Aalborg University Hospital, *"Elektronisk system adgang"* (ESA).

Data are stored in accordance with the stipulations in The Danish Personal Data Protection Act (Persondataloven) and other relevant Danish legislation. If any data processing would occur in foreign countries, the data will be anonymized and handled according to the Danish Data Protection Act.

The data can only be used for the interpretation of this project and will therefore not be of interest to third party.

The project is included in "Region Nordjyllands fællesfortegnelse".

VIII. STUDY LIMITATIONS

Both PTT and QST require corporation from the patients and include subjective measures of pain. As the measured thresholds are not purely objective, psychosocial factors might influence test results.

The study includes diabetic patients exclusively and might not be applicable on populations with different causes of neuropathy.

The expected number of participants are set at 80, thus maybe require additional larger studies to confirm findings.

IX. ETHICAL CONSIDERATIONS

A. Informed Consent

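### The main endpoint is accuracy per examination, but the analysis gives unvalidated accuracy per measurement, which leaves room for the comparison of methods to favour whichever offers more readings

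*Combined protocol and SAP*

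**What the plan says.** Section IV.A sets the endpoint at the level of the examination: "The main endpoint of the study will be sensitivity/specificity of all examinations", together with "a comparison of the newer methods against more well-established modalities".

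Section VI.B works at the level of the single measurement. In step 1, "a series of univariate LRM will be performed for each measurement to investigate the odds ratio and accuracy of the individual". Step 2 puts all measurements into one logistic model. Step 3 reduces the factors and assesses the accuracy of the reduced set.

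The examinations differ in how many readings they yield (IV.D):
- QST: "The protocol consists of seven tests measuring 13 parameters including".
- PTT: patch and pin electrodes, and "This procedure will be repeated a number of times using different electrodes". No total is given.
- MRI: a list of six components, ending with "6) MRI neurography of the peripheral nerve fibers". The number of derived indices is not given.

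The only diagnostic threshold in the plan is the entry criterion for groups 1 and 2 (IV.B): "Diagnosed with DPN defined as a threshold above 25-volt biothesiometry or absent feeling on the big toe using 10g-monofilament".

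The plan does not give a lead index per examination, cut-offs for the accuracy analysis, a rule for combining readings, the outcome variable of the logistic models, or any cross-validation or separate sample.

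**The concern.** To get from VI.B to the endpoint in IV.A, someone must decide which reading stands for each examination and where it is cut. The plan does not make that decision. If it is made after the per-measurement results are seen, the natural choice is the best reading. The best of several noisy estimates is too high on average, and the excess grows with the number of candidates. Two methods whose readings are equally good would then show different accuracy because one offers more readings.

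This differs from the problem of many significance tests, which VI.B tries to meet with a combined model. It also differs from overfitting of that combined model. It affects the ranking of single methods, which is part of the main endpoint. Step 3 raises a related issue: it is a selection that the plan does describe, and its accuracy is assessed in the same participants.

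**Working it through.** **Group sizes.** The formula in VI.A gives 15.7 × (4.7² + 7.5²) / (14.4 − 5.7)² = 15.7 × 78.34 / 75.69 = 16.25, printed as 16. Then 16 / 0.8 = 20 per group, and 4 × 20 = 80. This reproduces the plan's figures. Two groups have neuropathy and one diabetic group does not, so the contrast is 40 against 20 recruited, or 32 against 16 evaluable. The contrast is an assumption, because VI.B does not state the models' outcome.

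**Number of indices, k.** QST has 13 (documented). PTT is taken as 2 and MRI as 6; both are assumptions based on the electrode types and scan components listed.

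**True accuracy.** Every index is normal with a 0.8 SD shift. The true Youden index (sensitivity + specificity − 1) is 2Φ(0.4) − 1 = 0.31.

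**Simulation.** 1,500 runs per cell. The largest absolute Youden index is taken over all cut-offs and over the k indices, with a common correlation between indices of 0 to 0.5. Mean apparent Youden index at 40:20:

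| Indices | Apparent Youden | Excess over 0.31 |
|---|---|---|
| 1 | 0.41 | 0.10 |
| 2 | 0.46–0.48 | 0.15–0.17 |
| 6 | 0.52–0.55 | 0.21–0.24 |
| 13 | 0.55–0.60 | 0.24–0.29 |

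The first 0.10 comes from choosing the cut-off in the sample and is shared by all methods. The distortion between methods is the difference from the one-index row: 0.05–0.07 for two indices, 0.11–0.14 for six and 0.14–0.19 for 13. With 32:16 evaluable, the values are 0.43 for one index and 0.58–0.62 for 13. With no true ability at 40:20, they are 0.22 and 0.34–0.36.

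**Check on a measure that needs no cut-off.** A second simulation took a true AUC of 0.70 for every index, 40:20 and correlation 0.3 to 0.6. The mean best AUC was 0.70 (1 index), 0.73 (2), 0.76–0.78 (6) and 0.78–0.80 (13). An examination with several indices beat a single-index one whose reading was equally good in 66–67% (2 indices), 85–87% (6) and 91–93% (13) of simulated studies. A fair comparison would give 50%.

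**Check of the remedy.** With one index named beforehand, the mean AUC was 0.70 for both examinations. With index and cut-off both chosen inside 10-fold cross-validation, balanced accuracy was 0.63 for one index and 0.63–0.64 for 2 to 13, against a true 0.645. The advantage of having more readings fell to about 0.01 or less.

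**The case against.** **The plan does not say that the best index will be reported.** This stands. One model per measurement, with every result shown, favours no examination. A reader might infer that each examination's figure will be that of its best reading, but the documents only leave this possible. The one selection in writing is step 3.

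**The newer methods need not be the ones that gain.** This also stands. A reader might infer that the bias promotes PTT or MRI. However, the only documented count, 13, belongs to QST, which III and IV.A treat as established. PTT has two documented electrode types, and a count of two adds only 0.05–0.07 in Youden index (about 0.03 in AUC). MRI is under test in III but listed among established methods in IV.A.

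**Biothesiometry and monofilament are not disadvantaged examples.** They define neuropathy in IV.B. If group is the models' outcome, they look near-perfect by construction.

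**Equal accuracy per index is not equal accuracy per examination.** This is correct. Thirteen indices combined optimally have a shift of 0.8 × √(13 / (1 + 12ρ)) SD, where ρ is their correlation. That gives a true Youden index of 0.41 at ρ = 0.5, 0.50 at 0.3 and 0.85 at 0. But a best single index with its cut-off is not that combination. Its true value stays 0.31, so the figure reported for it is still inflated.

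**The plan admits its limits.** VIII says that larger studies may be needed for confirmation. That does not correct the ranking that this study would publish.

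**Conclusion.** The point holds in a conditional form. The endpoint is per examination, the analysis is per measurement, nothing links the two, and all accuracy is estimated in the participants used for fitting. If an examination is represented by its best index, the comparison favours examinations with more readings. The excess over a one-index test is 0.14–0.19 in Youden index for QST's 13 parameters. It is smaller for PTT and MRI under the assumed counts of two and six.

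The size rests on the 40:20 contrast, normal data, equal true accuracy of all indices, and a cut-off that maximises the Youden index; VI.B does not say how accuracy will be obtained. The AUC check shows that the effect of choosing the index does not depend on that last assumption. The direction for a given pair of methods depends on their counts: against QST, PTT would more likely lose. The documents do not support a claim that the new methods are systematically favoured.

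The plan should be changed, because the problem touches the main endpoint and is cheap to prevent.

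**What to change.** Add to VI.B one rule for every examination in the head-to-head comparison:

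1. Either name one index and its direction per examination before the accuracy analysis, or choose the index inside repeated 10-fold cross-validation.
2. In both cases, derive the cut-off inside the folds for all methods. Fixed cut-offs for some methods and data-derived ones for others would create a new asymmetry.
3. Apply the same cross-validation to the step 3 factor reduction, repeating the selection in each fold.
4. Base the comparison of methods only on these figures, and label all other per-index accuracies exploratory.

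The outcome of the logistic models must be stated as well, since the folds cannot be formed without it.

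The cost is a short list of indices or some programming; no participant, visit or measurement is added. The reported accuracy of examinations with many indices will be less favourable.

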The blood samples will be taken and handled as usual by the biochemical department and will be destroyed after usage. No biobank will be made. All samples will start being analyzed immediately (within 2h), however, some samples (like vitamin D) will take some time to analyze. All results will be available within 10-12 days but samples will always be destroyed as soon as the analysis has been initialized.

V. DATA COLLECTION

Patient data will be collected using the electronic patient journal (EPJ) after consent of the participant. Only patients with an active continuity of care at SDCN will be included (as well as healthy controls). The principle investigator is employed at SDCN as a medical doctor alongside one of the Ph.D.-students.

Data collected will include demographic data such as name, age, sex, weight, and height, and clinical information related to diabetes, such as type, duration, medication, complicating peripheral arterial disease, and status of complications. This to ensure correct grouping of the patients and to make sure that they meet the inclusion criteria.

VI. DATA ANALYSIS

A. Sample Size Considerations

The following sample size estimation is made on the ability to separate a group of diabetic patients without neuropathy from a group of diabetes patients with 'moderate' neuropathy. The calculations are based on published measurement of the sensory nerve action potential amplitude in nerve fiber conduction assessments[45]. Setting the significance level to 0.05 and the power to 0.8 results in a sample size estimation of 16 persons in each group. $n = \frac{15.7*\sigma^2}{d^2} = \frac{15.7*(4.7^2+7.5^2)}{(14.4-5.7)^2} = 16$. The study involves several experiment measures, but we expect that max 20% of the measures will be dropouts. The number of participants needed to be recruited in each group will therefore be $N = \frac{n}{1-dropout} = \frac{16}{0.8} = 20$. We want to compare four groups as defined in section IV.B. Study Population. The total number of participants will therefore be 80.

B. Statistical Methodology

The data will initially be analyzed by a series ANOVA test to compare each measurement between the four groups.

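### The three-step logistic regression does not prevent mass significance, and its combined accuracy from at most 80 people will be too optimistic

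*Combined protocol and SAP*

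**What the plan says.** Section VI.B (Statistical Methodology) opens with single-measurement tests: "The data will initially be analyzed by a series ANOVA test to compare each measurement between the four groups". No adjusted alpha, gatekeeping test or primary measurement is named.

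The remedy follows directly: "To avoid 'mass significance' a combined analysis of all measurements will be performed by logistic regression models (LRM) in three steps". The steps are:

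- Step 1: "First, a series of univariate LRM will be performed for each measurement to investigate the odds ratio and accuracy of the individual".
- Step 2: "Second, a multiple factor LRM with all measurements as factors will be performed to estimate the odds ratio and accuracy", here for all measures in combination.
- Step 3: "Thirdly, factor reduction will be performed to assess the accuracy and odds ratio of a set of independent measures".

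Bivariate correlations come next, and then "a further analysis of the interdependency of the measures using factor analysis will be performed". The section does not state the LRM outcome, the groups compared, the list of factors, the reduction rule, or any penalty, cross-validation, bootstrap or hold-out sample.

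Section IV.B, inclusion criterion 4, defines neuropathy (DPN) for groups 1 and 2: "Diagnosed with DPN defined as a threshold above 25-volt biothesiometry or absent feeling on the big toe using 10g-monofilament". Section VIII (Study Limitations) adds one caution: "The expected number of participants are set at 80, thus maybe require additional larger studies to confirm findings".

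**The concern.** The plan recognises the multiplicity problem and says that the LRM solves it. Fitting further models after an unadjusted series of tests does not lower the error rate of that series, and step 1 repeats the one-at-a-time approach. Step 1 names no significance test, so multiplicity applies there only if its odds ratios are tested.

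Steps 2 and 3 raise a different problem. A logistic model with many factors, fitted and judged on the same small sample, looks accurate even when the factors carry no information. A third problem depends on the unnamed outcome: if it is DPN as defined at inclusion, the factors include the two tests that define it.

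At stake is the reported accuracy of the tests in combination and of the reduced set, and which single measurements are called significant. Combined accuracy is a secondary output. The main endpoint in section IV.A, sensitivity and specificity of each examination, is not touched by the all-factor overfit where an examination yields one measure.

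**Working it through.** **Sample size.** Section VI.A: 15.7 × (4.7² + 7.5²) / (14.4 − 5.7)² = 15.7 × 78.34 / 75.69 = 16.25, stated as 16. Then 16 / 0.8 = 20 per group, and 4 × 20 = 80. The figure reproduces, but it was set for one two-group comparison of one nerve conduction measure, not for a multivariable model.

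**Number of factors (assumed, from section IV.D).**

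- Low count, one per modality: QST, PTT, pinprick, biothesiometry, monofilament, nerve conduction, CCM, axon flare, Vagus and MRI = 10.
- High count: QST 13 + PTT 2 + Vagus 4 + MRI 6 + one for each of the other six = 31.
- Cognitive, pressure and toe-oxygen measures would add more.

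With DPN against no DPN in diabetes (40/20), the smaller class holds 20/10 = 2.0 down to 20/31 = 0.65 people per factor. With controls pooled into the no-DPN class (40/40), it holds 4.0 down to 1.3.

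**Step 2 on pure noise.** 600 simulated datasets per cell, unpenalised maximum likelihood, true AUC 0.50, separation checked by linear programming (apparent AUC set to 1 if separated):

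| Contrast | Apparent AUC, 10 factors | Apparent AUC, 31 factors | Complete separation, 31 factors |
|---|---|---|---|
| 40/20, DPN vs none in diabetes | 0.75 | 0.98 | 82% |
| 40/40, controls pooled with no DPN | 0.70 | 0.88 | 2% |
| 20/20, painful vs painless | 0.79 | 1.00 | 100% |
| 60/20, diabetes vs controls | 0.73 | 0.94 | 38% |

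With 10 factors, separation occurred in 0–1% of datasets in all four contrasts. With a cut-off at group prevalence, apparent sensitivity/specificity (truth 0.50/0.50) ran from 0.67/0.69 to 0.97/0.97 at 40/20, and from 0.65/0.65 to 0.80/0.80 at 40/40. Without the two DPN-defining tests (8 to 29 factors), AUC was 0.72–0.97 at 40/20 and 0.68–0.86 at 40/40. Correlating 31 factors at 0.5 changed little (0.99 and 0.88).

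Real signals do not remove the gap. With three 0.7 SD signals at 40/20, apparent AUC was 0.90 against 0.71 in new data with 13 factors, and 0.99 against 0.65 with 25.

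**Step 3 on pure noise.** Five retained from 31 factors and refitted on the same data:

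- Chosen using the outcome: 0.80 (40/20) or 0.75 (40/40); 0.73 or 0.69 if factors correlate 0.5.
- Five principal components formed without the outcome: 0.67 or 0.64.

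**Circularity, if the outcome is DPN by criterion 4.** Code toe = 1 for absent feeling on the big toe. Since volts cannot be negative, volts + 26 × toe > 25 exactly when volts exceed 25 or toe = 1. That linear score is the definition, so the LRM separates the classes completely: 100% apparent accuracy and no finite odds ratios. This occurred in 400 of 400 datasets in each of six assumed settings. Section IV.D tests four monofilament spots. Volts plus a four-spot count separated 0.5–32% of datasets, with apparent AUC 0.93–0.99, so a four-spot score weakens exact separation but not the circularity. With nerve conduction as reference, this circularity would not arise; the overfit would.

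**Multiplicity, if every test uses 0.05 (stated only for sample size) and no group differs.**

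- Independent ANOVAs: 1 − 0.95¹⁰ = 0.40 and 1 − 0.95³¹ = 0.80.
- Correlation 0.3 to 0.7 (4000 simulated series per cell): 35% to 22% for 10 tests, 69% to 36% for 31.
- Univariate LRMs tested as well: 59–94% independent, 33–86% correlated.

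**The case against.** The strongest points against are these.

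- **Much is read from silence.** The outcome, factor list, reduction method and cut-off are unstated, and the plan does not rule out validation. The clinical tests might also be combined into one disability score, which would change the factor list. This stands as a reason to give ranges. It does not rescue the plan: the low end of the range still shows an AUC of 0.70 from noise.
- **Reduction may be blind to the outcome**, as the planned factor analysis makes plausible. The optimism is then smaller (0.64–0.67) but still present.
- **The 40–80% assumes that nothing differs.** Biothesiometry and monofilament differ by definition, and nerve conduction is expected to differ. Leaving these three out gives 1 − 0.95⁷ = 0.30 to 1 − 0.95²⁸ = 0.76, a modest change.
- **Benjamini-Hochberg controls the false discovery rate, not the chance of any false positive.** This is correct. With true signals added, any false positive still occurred in 16–39% of simulated studies, against 60–89% unadjusted, while the false discovery rate stayed at 3–5%.
- **The main endpoint is not wholly safe.** One sensitivity and specificity for QST (13 parameters) or multi-sequence MRI might need a combined model and would then inherit the overfit. If DPN is the outcome, step 1 also scores the two defining tests against themselves: at 25 V, biothesiometry has 100% specificity by construction. Both points are fair; the second is separate from the combined-model problem.
- **The limitations section concedes that larger studies may be needed.** That is a caveat on interpretation and corrects none of the reported figures.

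**Conclusion.** The concern holds. As written, the three-step LRM does not control multiplicity, and its combined accuracy would be materially overstated.

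Confidence is high for the overfit: it appears in every contrast and factor count examined, ranging from moderate-looking with 10 factors to near perfect with 31 at 40/20. The multiplicity figures depend on testing at 0.05, on how many measurements truly differ, and on their correlation. The circularity depends on DPN by criterion 4 being the LRM outcome. The factor counts and contrasts are assumptions, because the plan gives neither.

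**What to change.** Amend section VI.B as follows.

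1. Name the LRM outcome and the analysis set.
2. If the outcome is DPN by criterion 4, leave biothesiometry and monofilament out of steps 2 and 3.
3. Fit step 2 with a ridge penalty and label its odds ratios as shrunken.
4. Keep step 3, but prespecify how many measures are retained and whether the outcome is used to choose them.
5. For both steps, report AUC, sensitivity and specificity from repeated 5-fold cross-validation, repeating scaling, tuning and reduction within each training fold and fixing the cut-off rule in advance.
6. Apply Benjamini-Hochberg at 5% to the single-measurement tests, as one family if both the ANOVAs and the univariate LRMs are tested.
7. Delete the statement that the LRM avoids mass significance.

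The fix was checked with 8 and 29 factors, at 40/20 and 40/40, with correlation 0 and 0.5 (120 datasets per cell). On noise, mean cross-validated AUC was 0.49–0.52 for ridge, five components and best five. With five 0.8 SD signals, it lay within 0.02 of the AUC in 3000 new subjects for all three (ridge 0.80–0.90 against 0.81–0.90). The penalty alone is not enough: apparent ridge AUC on noise was 0.64–0.87. If no measurement differs, pooled Benjamini-Hochberg gives any false positive in 3–6% of studies; applied separately to the two series, it gives 5–10%.

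The cost is SAP wording and modest programming, with no new data. Reported accuracy will be lower, fewer single measurements will be significant, and the ridge odds ratios will be shrunken and lack standard confidence intervals. The cross-validated AUC will be imprecise (SD 0.04–0.12 between simulated studies). The check used complete data, so the SAP must also say how missing measurements enter the combined models.
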